Summary of planned clinical study Alanine aminotransferase (ALT) >2x upper limit of normal (ULN) Ongoing requirement for blood and/or platelet transfusion A subject may be considered for dose escalation (after at least 3 months of treatment) if, in addition to the criteria above, they meet the below criteria: Any other clinically important manifestation of LAL Deficiency on either clinical examination, laboratory assessment, or imaging which has either not improved from baseline o improved and plateaued but has not normalized The definition of a plateauing of effect requires consideration of a minimal of 3 assessments) failed to normalize within 12 months of initiation of treatment Manifestations include but are not restricted to the following: A decrease in weight for age defined as crossing >2 major centile lines on standard weight for age curves, serum transaminases, albumin <3.5 g/dL, hepatomegaly, splenomegaly or lymphadenopathy If the subject continues to demonstrate evidence of the above specified criteria after at least 4 infusions at a dose of 3 mg/kg gw, the Investigator, may request of the Sponsor (in consultation with the SRC) to increase the dose up to a maximum of 5 mg/kg gw on a case by case basis. In the rare circumstance a dose escalation to 5 mg/kg may be considered prior to 4 infusions if agreed to by the Sponsor and SRC. **Controls** There is no placebo or comparator in this study. No therapy has been shown to be safe or effective for the treatment of LAL Deficiency. Hematopoietic stem cell transplantation has been used Rescue treatment experimentally but has a high morbidity and mortality in this patient population. Safety Safety endpoints will include the incidence of adverse events (AEs), serious adverse events (SAEs), and IARs; changes from baseline clinical laboratory tests; changes in vital signs (blood pressure, heart rate, respiratory rate, and temperature) during and post-infusion relative to pre-infusion values; physical examination findings; use of concomitant medications/therapies; and characterization of ADAs, including ADA positivity rate, time to ADA positivity, median and peak ADA titer, and time to peak ADA titer. The impact of ADAs on safety endpoints will also be explored. characterization of ADAs, including inhibitory and/or neutralizing ADAs and measurement of specific ADA subtypes (e.g., IgE), may be performed, if Criteria for evaluation appropriate. **Efficacy** Survival endpoints will include proportion of subjects surviving to 12, 18 and 24 months of age, and other timepoints, as data permit, and estimated median age at death. Survival rates and median age at death derived from this study will be compared to rates/times reported in the literature and previous studies. Other efficacy endpoints will include changes from baseline in percentiles and/or z-scores for WFA, WFL/WFH, and LFA/HFA and the corresponding growth status indicators of underweight, wasting, and stunting, as well as changes from baseline in z-scores for head circumference-for-age (HCFA)

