1.5.2 Risk/Benefit Assessment

LAL Deficiency is a very rare disease with no safe or effective therapies. LAL Deficiency presenting in infants results in significant morbidity and death typically within 6 months of age (Assmann, 2001, *The Metabolic and Molecular Basis of Inherited Disease*).

Page 22 of 66

No significant toxicities were identified in pre-clinical pharmacology and toxicology studies at doses equivalent to and substantially greater than the planned doses for the current study (Refer to IB for details).

Clinical experience with sebelipase alfa in adult subjects with LAL Deficiency treated in study LAL-CL01 and LAL-CL04 indicates that sebelipase alfa is well tolerated at doses ranging from 0.35 mg/kg qw to 3 mg/kg qw and produces rapid improvements in serum transaminases and other evidence of biological activity. Sebelipase alfa has also demonstrated an acceptable safety profile and positive treatment effects in infants receiving doses up to 3 mg/kg qw on in study LAL-CL03. See Section 1.4 and the IB for further details on the clinical experience with sebelipase alfa. Thus, there is a reasonable basis to conclude that sebelipase alfa therapy in this study will be well tolerated and associated with beneficial effects on disease activity.

In addition to clinical experience with sebelipase alfa, extensive human experience exists for ERTs in the treatment of other lysosomal storage disorders including Gaucher, Pompe, and Fabry disease. The main unfavorable effects associated with administration of approved ERTs (including but not limited to Cerezyme®, VPRIV®, Myozyme®/Lumizyme®, Fabrazyme®) are IARs, which typically occur during or within several hours following completion of the infusion and are usually mild and can be managed by changes in infusion rate and/or the administration of antipyretics and antihistamines. Severe infusion reactions including anaphylaxis, and SAEs related to ERT administration occur rarely and can require intensive medical intervention. Given the propensity for infusion reactions with ERT administration, measures have been incorporated in this protocol to minimize risk and monitor subject safety.

Anti-drug antibodies (ADAs) have been reported with approved ERTs and these may be associated with altered response to treatment and/or increased risk of infusion reactions.

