Given the severity and life threatening nature of rapidly progressive LAL Deficiency, it is likely that these subjects will be hospitalized during the first several weeks on study. For the subjects who are stable enough to be treated on an outpatient basis, safety follow-up assessments for AEs will be conducted by telephone 24 hours following the first 2 infusions of 1 mg/kg qw and 3 mg/kg qw, as applicable.

Subjects who appear to have an acute illness (e.g., upper respiratory infection or febrile illness) should have their scheduled infusions postponed by up to 2 days (up to 5 days if subject is on a qow infusion schedule) to allow for resolution. If the illness persists for longer than 2 days (5 days if subject is on a qow infusion schedule), the infusion schedule should reset to the next scheduled infusion after the subject's recovery. The Investigator may conduct an unscheduled visit at any time during the study at his/her discretion. Assessments performed at this visit should be symptom directed. Safety laboratory testing may be performed if the Investigator considers it necessary. Repeat laboratory testing may be needed based on results from the

unscheduled laboratory testing. If the subject is discontinued from study treatment at a scheduled visit or at an unscheduled visit, the subject should return no earlier than 7 days after the last dose of IMP for an End of Study assessment.

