3.1.1.2 Dose escalation after at least 3 months of treatment

- In addition to the criteria in Section 3.1.1.1, any other clinically important manifestation of LAL Deficiency on either clinical examination, laboratory assessment, or imaging which has either
 - not improved from baseline
 - o improved and plateaued but has not normalized
 - (Note: The definition of a plateauing of effect requires consideration of a minimal of 3 assessments)
 - o failed to normalize within 12 months of initiation of treatment

Manifestations include but are not restricted to the following: A decrease in weight for age defined as crossing ≥ 2 major centile lines on standard weight for age curves, serum transaminases, albumin <3.5 g/dL, hepatomegaly, splenomegaly or lymphadenopathy. If the subject continues to have criteria for dose escalation after at least 4 infusions at a dose of 3 mg/kg qw, the Investigator may request of the Sponsor (in consultation with the Safety Committee) to increase the dose up to a maximum of 5 mg/kg qw on a case by case basis. In rare circumstances, a dose escalation to 5 mg/kg may be considered prior to 4 infusions, if

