4.8 Subject Recruitment and Screening

Subjects may be recruited into the study directly from the Investigators' or sub-investigators' clinical practices, or referred to the investigative sites from other clinics. Information about the study will be posted on the http://clinicaltrials.gov/ and https://www.clinicaltrialsregister.eu/websites.

Subject screening should occur between 0 and 21 days prior to the infusion at Week 0 (Day 0). Prior to any screening procedures, a subject needs to be registered with the Sponsor.

5 Schedule of Assessments and Study Procedures

The schedule of assessments, Screening through Follow-up, is presented in Appendix A. All visits will be calculated from Week 0; consecutive infusions must be administered at least 5 days apart. Additional details regarding the visit schedule and the timing of study procedures are provided in the Study Operations Manual (SOM).

Subjects who are clinically stable enough to tolerate general anesthesia may be considered for central line placement for long-term vascular access, in accordance with institutional guidelines. Magnetic resonance imaging (MRI) should be considered for subjects receiving general anesthesia and/or sedation for central line placement or for other procedures (see Section 5.1.8).

Subjects who are medically stable, as determined by the Investigator, may transfer to a local medical center for long-term treatment, contingent upon the local medical center having been approved and having secured the required regulatory, IRB/IEC, and Sponsor approvals. Scheduled study assessments may also be performed at a local medical center with access to the appropriate facilities and expertise.

Local analgesic cream (e.g., eutectic mixture of local anesthetics) will be allowed at least 20-30 minutes (or according to applicable institutional guidelines) prior to IV placement or blood sampling.

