Appendix A: Schedule of Assessments

	Screening	Screening Treatment Phase [*]																
Assessments	Day -21 to Day -1	W 0 ¹⁰	W 1	W 2	W 3	W 4	W 5	W 6	W 7	W 8	W 9	W 10	W 11	W 12	W 13	W 14	W 15	W 16
		± 2 days	± 2 days	± 2 days	± 2 days	± 2 days	± 2 days	± 2 days	± 2 days	± 2 days	± 2 days	± 2 days	± 2 days	± 2 days	± 2 days	± 2 days	± 2 days	± 2 days
Informed Consent	Х						-											
Inclusion/Exclusion	Х	Х																
Medical/Family History	Х																	
Physical Exam ²	Х				Х						Х						Х	
Anthropometrics ³	Х	Х	Х	Х	Х	Х	Х	Х	Х	Х	Х	Х	Х	Х	Х	Х	Х	Х
Vital Signs ⁴	Х	Х	Х	Х	Х	Х	Х	Х	Х	Х	Х	Х	Х	Х	Х	Х	Х	Х
12-lead ECG	Х	If clinically indicated																
Denver II	Х																	
Abdominal Ultrasound		Х												Χ				
Abdominal MRI ⁵	X															Χ		
Clinical LabTests ^{6, 7}	Х	XP	XP	XP	XP	XP				XP								
Exploratory Biomarkers ⁷	X			Х						Х				Χ				X
DNA Sample (subject) ^{7, 8}	X																	
DNA Sample (parents)	X																	
PK Sample ^{7, 9}		X'																
DBS LAL Activity 7	X																	
Sebelipase Alfa Dosing ¹		Х	Х	Х	Х	Х	Х	Х	Х	Х	Х	Х	Χ	Х	Х	Х	Х	Х
Anti-drug Antibody 7	X X X X X X X X X X X X X X X X X X X								X									
Adverse Events		CONTINUOUS																
Concomitant Therapies	CONTINUOUS																	

^{*} All visits will be calculated from Week 0; consecutive infusions must be administered at least 5 days apart. Day 0 assessments do not need to be repeated if they have been conducted within the 3 days prior to Screening

P Pre-dose

- 1 For the subjects who are stable enough to be treated on an outpatient basis, safety follow-up assessments for AEs will be conducted by telephone 24 hours following the first 2 infusions of 1 mg/kg qw, and 3 mg/kg qw
- 2 All physical examinations will include liver, spleen, and lymph node assessments and digital photographs (full length and abdominal close up) (see Section 5.1.6).
- 3 Weight, recumbent length or height, and abdominal circumference will be measured at all visits; head and mid-upper arm circumference will be measured at Screening, Weeks 0, 4, 8, 12, and 16.
- 4 During infusion visits, vital signs will be measured pre-dose, every 15 (±5) minutes during the infusion, and every 30 (±10) minutes from 0 to 4 hours post-infusion (see Section 5.1.9).

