# 4. **Description of the Protocol**

LAL-CL08 is a phase 2, open-label, multicenter study to evaluate the safety, tolerability, efficacy, and pharmacokinetics of sebelipase alfa (SBC-102) in infants with rapidly progressive Lysosomal Acid Lipase Deficiency (LAL-D).

Following a screening period of up to 3 weeks, each eligible patient will receive an intravenous (IV) infusion of SBC-102 at an initial dose of  $1\text{mg}\cdot\text{kg}^{-1}$  every week (qw). During the first 3 months of treatment after at least 4 doses of  $1\text{mg}\cdot\text{kg}^{-1}$ , a dose escalation to 3 mg·kg qw may be considered for a subject who satisfies the criteria outlined in Section 3.1.1 of the study protocol. After 3 months of treatment, subjects who satisfy additional criteria may be escalated to a dose of either 3 mg·kg qw or 5 mg·kg qw depending on current dose. Subjects who are on treatment for at least 96 weeks and are on a stable dose for at least 24 weeks may be considered to transition to an every other week (qow) dosing schedule. The duration of each subject's treatment in the study is expected to be at least 18 months, and subjects may continue to receive treatment in the study for up to 3 years. The overall duration of a subject's participation in the study, inclusive of a 3-week screening period and a 4-week follow-up period, may be up to 3 years and 7 weeks.

The primary objective of the study is to evaluate the safety and tolerability of SBC-102 in infants with rapidly progressive LAL-D.

The secondary objectives are:

- To evaluate the effect of SBC-102 therapy on:
  - Survival at 12 months of age
  - Survival past 12 months of age
  - Growth parameters
  - Hepatomegaly, splenomegaly, and liver function
  - Hematological parameters
  - Characterize the PK of SBC-102 delivered by IV infusion

The exploratory objectives are:

- To determine the effects of SBC-102 on lipid parameters
- To assess the effects of SBC-102 on achievement of developmental milestones
- To evaluate potential disease-related biomarkers

An independent Safety Review Committee (SRC) will oversee safety in this study. The SRC will review available safety data during at least semiannual periodic meetings and on an ad hoc basis, as needed, in the event of unanticipated safety findings.

Further details on target population, inclusion/exclusion criteria, schedule of assessments and study procedures are available in the study protocol.

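### The next-day outpatient AE call is scheduled at 1 and 3 mg/kg qw but not at 5 mg/kg qw, the highest dose the protocol permits

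*Protocol*

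**What the plan says.** Section 3.1 provides that subjects stable enough to be treated as outpatients have a safety follow-up for AEs by telephone at 24 hours, "following the first 2 infusions of 1 mg/kg qw and 3 mg/kg qw, as applicable". Appendix A footnote 1 repeats the rule: the assessments are "conducted by telephone 24 hours following the first 2 infusions of 1 mg/kg qw, and 3 mg/kg qw".

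The permitted doses go further. Under Section 3.1.1.2, if escalation criteria persist after at least 4 infusions at 3 mg/kg qw, the Investigator may put a further step to the Sponsor for approval: "in consultation with the Safety Committee) to increase the dose up to a maximum of 5 mg/kg qw on a case by case basis". Earlier escalation to 5 mg/kg is possible in rare circumstances if the Sponsor and the committee agree. The synopsis carries the same provision ("to increase the dose up to a maximum of 5 mg/kg"). SAP Section 4 restates it ("After 3 months of treatment, subjects who satisfy additional criteria may be escalated to a dose of either"), giving the levels as 3 or 5 mg/kg qw according to the dose the child is on.

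On prior human experience, Section 1.5.2 describes the product in adults as "well tolerated at doses ranging from 0.35 mg/kg qw to 3 mg/kg qw", and reports an acceptable safety profile "in infants receiving doses up to 3 mg/kg qw".

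**The concern.** The call is more than a first-exposure precaution. The protocol repeats it at 3 mg/kg qw in children who have already tolerated 1 mg/kg qw, so its evident purpose is closer AE ascertainment at each new dose level. It stops one level short of the top, and no reason is given.

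Three features of the protocol suggest the call is needed at least as much at 5 mg/kg:

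- The human experience the protocol summarises ends at 3 mg/kg qw (Sections 1.5.1 and 1.5.2).
- Section 1.5.1 foresees doses above 3 mg/kg qw only if neutralizing antibodies cause a loss of efficacy. Section 1.5.2 notes that antibodies to approved enzyme replacement therapies may go with a higher risk of infusion reactions. Section 3.1.1.2 does not make antibodies a condition of escalation, but the case the Sponsor anticipates is one of higher risk.
- Section 3.1 expects hospitalization in the first several weeks. The 5 mg/kg provision sits under escalation after at least 3 months, so outpatient status is more likely at this step.

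Safety and tolerability are the primary objective. What is at stake is how soon a delayed reaction comes to the site's attention. The Investigator's 24-hour reporting clock (Sections 7.2.1 and 7.4.1) starts at first knowledge, so later contact can also delay reporting.

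**Working it through.** The plan states no figure to reproduce. The check compares the dose levels permitted with those the call covers, then works out the timing.

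**Coverage**

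| Weekly dose | Permitted by | Scheduled 24-hour calls for an outpatient |
|---|---|---|
| 1 mg/kg | Section 3.1 | 2 |
| 3 mg/kg | Sections 3.1 and 3.1.1 | 2 |
| 5 mg/kg | Section 3.1.1.2, synopsis, SAP Section 4 | 0 |

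Two of three permitted weekly levels are covered, and the uncovered one is the highest. The qualifier at the end of the Section 3.1 sentence selects whichever of the two named doses the child receives; it does not add a third.

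**What else applies at 5 mg/kg**

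- Vital signs (Section 5.1.9) are taken during the infusion and for 4 hours afterwards. This may be cut to 2 hours after at least a year without moderate-to-severe infusion-associated reactions, and no reset on a dose increase is stated.
- Dose-change laboratory tests (Section 5.1.11.2) are taken before the change and then at 4, 8 and 12 weeks.
- AE questioning (Section 7.3) takes place at each contact. Without the call, the next scheduled contact is the next infusion.
- Unscheduled visits (Section 3.1) are at the Investigator's discretion.

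None of these puts a scheduled AE contact between the end of on-site observation and the next infusion visit.

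**Timing of the first scheduled AE contact after the infusion day**

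Inputs: weekly visits are 7 days apart, each with a window of ±2 days (Appendix A); "consecutive infusions must be administered at least 5 days apart" (Section 5); the call, where required, falls on day 1.

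- Shortest gap: max(5, 7 − 2 − 2) = max(5, 3) = 5 days
- Nominal gap: 7 days
- Longest gap from windows alone: 7 + 2 + 2 = 11 days

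Delay relative to a day-1 call: 5 − 1 = 4 days, 7 − 1 = 6 days, and 11 − 1 = 10 days.

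**Size of the dose step**

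5 / 3 = 1.67. This is a ratio of doses, not of exposure or risk. In adults, Section 1.4.1 reports that AUC and Cmax rose more than proportionally to dose from 1 to 3 mg/kg, so exposure at 5 mg/kg cannot be assumed to be only 1.67 times that at 3 mg/kg.

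**Calls added by the fix**

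2 infusions × 1 call = 2 per outpatient escalated to 5 mg/kg qw.

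**The case against.** The omission is plain on the text, so the case on the other side is about weight.

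- **Rare and individually reviewed.** Doses above 3 mg/kg qw are not expected to be needed routinely, and up to 10 children will be enrolled. The step to 5 mg/kg goes to the Sponsor in consultation with the safety committee, whereas the step from 1 to 3 mg/kg needs only Investigator and Sponsor approval. Extra follow-up could be set child by child.
- **Prior tolerance.** A child normally reaches 5 mg/kg after at least 4 infusions at 3 mg/kg.
- **The main acute risk is watched on site.** Section 7.1.3 says most acute reactions to similar products occur within 2 hours of the infusion, inside the observation period. Later events would be ascertained late rather than lost. From the third infusion at 1 or 3 mg/kg the protocol already accepts weekly contact.
- **Other support exists.** Section 1.3 reports no meaningful toxicity at up to 50 mg/kg qw for 4 weeks in rats and monkeys, and good tolerance of up to 30 mg/kg qw for 6 months in juvenile monkeys. Further clinical data are in the Investigator's Brochure and further visit detail in the Study Operations Manual, neither of which is available here.
- **Cost.** Section 11 requires amendments to be signed by the Investigator and approved by the IRB/IEC, across approximately 5 primary centers.

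Most of this stands as a reason to grade the point low. None of it replaces the call. Prior tolerance of 1 mg/kg did not remove the call at 3 mg/kg. Committee consultation makes extra follow-up possible but does not require it. On-site observation ends within hours at every dose, including the two where the call is nevertheless required.

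**Conclusion.** The concern holds, at minor severity. As written, the highest permitted weekly dose lacks the next-day check given at both lower doses. An outpatient newly at 5 mg/kg has no scheduled AE contact between the end of infusion-day observation and the next infusion, nominally 6 days later than the call would be (4 to 10 days).

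This assumes that the child is an outpatient on weekly dosing, that the next infusion is given within its window, and that the Study Operations Manual adds no call of its own. The range covers visit windows only; a missed infusion would lengthen it. The documents do not say how many children will reach 5 mg/kg as outpatients, and the number could be zero, so the effect is stated per child. The gap concerns the timing of AE ascertainment and changes no endpoint definition or planned analysis.

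**What to change.** In Section 3.1 and in Appendix A footnote 1, require the 24-hour telephone AE assessment for outpatients after the first 2 infusions at each new dose level, and name 5 mg/kg qw explicitly. Wording tied to each new level avoids having to keep a list of doses in step with the escalation rules.

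The running cost is at most 2 telephone calls per outpatient escalated to 5 mg/kg qw. The documentary cost is two wording changes, which need a protocol amendment with IRB/IEC approval and are best bundled with the next one. No change to the SAP is needed.

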3.1.1 Dose Escalation

The Investigator, in consultation with the Sponsor, will monitor subjects for evidence of the below specified criteria that may reflect a need for a dose increase. These considerations should include evaluation of other potential causes of any clinical manifestations that are thought to negatively impact these criteria. Other causes could include:

- missed study infusions
- initiation of a potentially hepatotoxic concomitant medication in a subject with elevated ALT
- concomitant illness in a subject with reduced weight gain such as an upper respiratory tract infections or other childhood viral infection

3.1.1.1 Dose escalation criteria during first 3 months of treatment

During this period, a subject may be considered for dose escalation if he/she meets 2 or more of the following criteria at a dose of 1 mg/kg gw:

- Failure to gain an average of 5 g/kg body weight per day AND the presence of one or more of the following:
 - weight-for-length (WFL) or weight-for-height (WFH) z-score <-2 based on World Health Organization (WHO) child growth standards; and/or
 - length-for-age (LFA) or height-for-age (HFA) z-score <-2 based on WHO child growth standards
 - weight-for-age (WFA) z-score <-2 based on World Health Organization (WHO) child growth standard
- Albumin <3.5 g/dL
- Alanine aminotransferase (ALT) >2x upper limit of normal (ULN)
- Ongoing requirement for blood and/or platelet transfusion

